 2. For patients that present for delivery at a gestational age less than 34 weeks, it will be recommended that they discard their breast milk until 24 hours after their last TXA administration.
 3. Order TXA for patient in ESSENTRIS
 4. RN to pull TXA from Pyxis and put in patient's room
 5. TXA per protocol (see supplement A)
 6. The use of additional uterotonics or single additional dose of TXA is at the discretion of the delivering provider
 7. For patient monitoring protocol please see Supplement B.
 8. All neonates are monitored for a minimum of 24 hours either by the NICU or the Newborn Nursery. Vitals are taken every four hours. Weights and bilirubin levels are obtained daily. Daily physical exams are performed.
3. Data collection
 1. Participants will be assigned an individualized subject number upon their enrollment to the study.
 2. Participants will be followed from their enrollment into the study until six weeks postpartum.
 3. An Excel spreadsheet will be used to collect the variables as listed above.
 4. Once the variable collection is complete, the information will become de-identified.

5. Chart review will be performed to estimate institutional rates of the secondary outcomes in the 12 months preceding the initiation of the protocol.
4. Data Analysis
 1. SPSS software will be used for our statistical analysis. Normal distribution will be assumed given the intended number of patients for analysis. Categorical variables will be analyzed using the Chi-square test. The t-test will be utilized for the comparison of continuous interval data.
 2. Using a postpartum hemorrhage rate of 2.86% (institutional data), and a desired impact of reducing the hemorrhage rates by 50% after implementation of the new protocol, then 890 subjects would need to be recruited to answer the question.
 3. The secondary outcomes will also be tested against institutional rates. Institutional rates will be estimated by record sampling done at the time of data collection.

Experimental Procedures:

See supplement A

Research materials collected:

Variables to be collected:

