- Rare events from worldwide post marketing reports have included thromboembolic events (e.g., deep vein thrombosis, pulmonary embolism, cerebral thrombosis, acute renal cortical necrosis, and central retinal artery and vein obstruction), convulsion, chromatopsia, and visual impairment

Radiation/Laser Exposure: None

Justification/Minimization of Risks:

All identifiers will remain in the protected medical record. Any PHI extracted as a result of this study will be destroyed at the earliest opportunity consistent with conduct of the research, unless there is a health or research justification for retaining the identifiers or such retention is otherwise required by law. Protected health information will not be reused or disclosed to any other person or entity, except as required by law, for authorized oversight of the research study, or for other research for which the use or disclosure of protected health information would be permitted by approval of the IRB.

The current Maternal Child Executive Committee Policy on Tranexamic Acid (TXA) Administration will be followed to minimize any risks of harm to subjects.

Benefits:

Potential benefits of the research to the subject include a reduction in blood loss from delivery, decreased need for uterotonic medications, decreased need for blood transfusion, and less morbidity as a result of symptomatic anemia, resulting in increased satisfaction with the postpartum experience and increased maternal-neonate interactions.

Potential benefits of the research to the community/society included less overall maternal morbidity/mortality as well as a decreased demand on limited resources (i.e. blood products, uterotonic medications, time of additional healthcare providers, etc).

Requirements for Research Monitor:

Research Monitor Responsibilities:

Serves as a medical monitor, reviewing AEs as they are discovered to determine if the events suggest a trend toward increased risk to subjects that would require additional safeguards, subject notifications, or an invoking of stopping rules.

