Rates of hysterectomy – the number of patients requiring hysterectomy divided by the total number of deliveries

Admission to the Intensive Care Unit (ICU) - the number of patients requiring admission to the intensive care unit secondary to excessive blood loss divided by the total number of deliveries

Neonatal outcomes – incidence of fetal anemia, infection, hyperbilirubinemia, neurologic outcomes, and neonatal intensive unit admissions

Maternal mortality – incidence of mortality

Additionally, postpartum hemorrhage risk assessment will be utilized to stratify patients with regard to primary and secondary outcomes.

- Patients will be risk stratified to one of three risk categories depending on admission and intrapartum risk factors
 - High Risk Factors:
 - Placenta previa/ low lying placenta
 - Suspected accreta or percreta
 - Platelet count <70,000
 - Active bleeding
 - Known coagulopathy
 - Two or more medium risk factors
 - Medium Risk Factors:
 - Prior cesarean delivery, uterine surgery, or multiple laparotomies
 - Multiple gestation
 - > 4 prior births
 - Prior obstetric hemorrhage
 - Large myomas
 - EFW >4000
 - BMI > 40
 - Hct < 30%
 - Chorioamnionitis
 - >24 hours on Oxytocin
 - Magnesium sulfate
 - Low Risk: all patients not falling in the medium or high risk categories

Importance to Navy Medicine:

Beyond the potential impact that this study has in the reduction of maternal morbidity and mortality, it can also allow for perspective into resource management. Some of the Navy Military Treatment Facilities (MTFs) have limited blood bank stock, and massive hemorrhages requiring ongoing transfusion of products can quickly deplete the entirety of the supply. If we can find a solution that will reduce the number of instances where transfusion is necessary we can help to preserve limited resources. Likewise, this preventive measure will also have the potential to (cost) reduce the need for additional uterotonics, personnel, supplies and ICU beds.

There will be no collaboration with outside institutions.

Supplement A: TXA Protocol Administration (Modified from the NMCS Maternal Child Executive Committee's Policy)

1. TXA comes in a 1000 mg/10 mL vial. Nursing staff will pull this from the Pyxis at the same time they bring Oxytocin into the L&D room.
2. Add 1000 mg (or 1 vial) of 1000 mg/10 mL to 100 mL normal saline (100 mg/mL)
 - a. Bolus: 1 gram IV over 10 minutes
 - i. Set infusion pump rate to 600 mL/hr

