3. Begin the TXA infusion directly following umbilical cord clamping for the intent of preventing postpartum hemorrhage.
 - a. The TXA may be run as a secondary line (i.e. is compatible with pitocin) per [name], Chairman of the Pharmacy Department
4. TXA should be administered in a separate IV line from blood products.
5. Two-person verification is required (this can be a second nurse or can be the physician or certified nurse midwife that is attending the delivery)
6. A single additional dose of TXA (1 gram IV over 10 minutes) can be repeated after 30 minutes if bleeding continues or if bleeding stops and then re-starts within 24 hours of the first dose (for a maximum dose of 2g in 24 hours). This additional dose is considered a treatment dose. This additional dose is not required by the study design, which is to assess TXA in the *prevention* of hemorrhage.

Supplement B: Patient Monitoring following delivery

1. After delivery patients will be observed on the Labor and Delivery floor for a minimum of one hour. Thereafter they will be transferred to the postpartum ward where they will be observed for a minimum of 24 hours.
2. The following physical assessments will be completed every 15 minutes x 1 hour , then every 30 min x 2 hours, then every 4 hours until discharge.
 - A. Vital signs: BP and pulse as above. Temperature Q1 hour (after 2 normal values will space to Q4 hours).
 - B. Fundal assessment: Placement and tone
 - C. Lochia assessment: Color, with or without clots, amount
 - D. Perineum assessment: Intactness (approximation of tissues/wound/lacerations), hematomas, swelling
 - E. Bladder assessment: Distention, voiding (noting/documentation of most recent void/amount, spontaneous/catheterization).
 - F. Any symptoms that the patient reports.
3. The nursing staff will immediately report any findings that are not within normal limits to the delivering provider or on-call provider:
 - A. BP systolic > 160 or < 100
 - B. BP diastolic > 90 or <50
 - C. Pulse > 100
 - D. Nausea, dizziness or SOB
 - E. Moderate to copious lochia
 - F. Increased swelling or pain in vagina or perineal/rectal area
 - G. Distended bladder not relieved by catheterization or patient voiding
 - H. Fundus displaced or above umbilicus (if differs from initial normal placement of uterus), unrelieved with empty bladder.
4. Documentation
 - A. All assessments are documented in Essentris. See below for notes needed:
 - B. Complete intake and output flow sheet

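### Supplement A prints 100 mg/mL after the step that dilutes the TXA vial; that is the undiluted vial strength, and the prepared bag is about 9.1 to 10 mg/mL

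*Combined protocol and SAP*

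**What the plan says.** Supplement A is the working dosing instruction. Study Procedures, under Implementation on L&D, sends staff there: "TXA per protocol (see supplement A"). The Experimental Procedures section likewise only refers to Supplement A.

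The relevant lines of Supplement A are:

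- Item 1, the supply: "TXA comes in a 1000 mg/10 mL vial".
- Item 2, the preparation: "Add 1000 mg (or 1 vial) of 1000 mg/10 mL to 100 mL normal saline (100 mg/mL").
- Item 2a, the dose and time: "Bolus: 1 gram IV over 10 minutes".
- Item 2a.i, the rate: "Set infusion pump rate to 600 mL/hr".
- Item 5, the check: "Two-person verification is required".
- Item 6, the optional repeat dose, with the same amount and time: "A single additional dose of TXA (1 gram IV over 10 minutes) can be repeated after 30 minutes".

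No other part of the document states a concentration for the prepared bag. The section on justification and minimization of risks adds that "The current Maternal Child Executive Committee Policy on Tranexamic Acid (TXA) Administration will be followed". That policy is not reproduced, and the heading of Supplement A says the supplement is a modified version of it.

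**The concern.** Adding a 10 mL vial to 100 mL of saline must lower the concentration roughly tenfold, yet the figure printed after the dilution step is the one that applied before it. The vial strength already appears in the same line as milligrams per 10 mL, so a reader will naturally take the closing parenthesis as describing the mixture.

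If so, the sheet contradicts itself: the printed concentration and the printed pump rate cannot both describe the same bag. Anyone who labels the bag, verifies it or sets the pump by the printed concentration would be working from a figure at least ten times too high, and the two people checking the dose would hold two conflicting numbers. What is at stake is the dose a woman receives immediately after delivery.

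**Working it through.** **Inputs, all from Supplement A**

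- Vial: 1000 mg in 10 mL (item 1)
- Diluent: 100 mL saline (item 2)
- Printed concentration: 100 mg/mL (item 2)
- Dose and time: 1000 mg over 10 minutes (item 2a)
- Pump rate: 600 mL/hr, which is 10 mL/min (item 2a.i)

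**Step 1. Where the printed figure comes from.** Concentration = drug amount / volume.

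- Vial alone: 1000 / 10 = 100 mg/mL. This reproduces the printed figure.
- Vial added to a full bag: 1000 / (100 + 10) = 9.09 mg/mL.
- Final volume of 100 mL (10 mL withdrawn first, or the vial volume ignored): 1000 / 100 = 10 mg/mL.

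Only the undiluted vial gives 100 mg/mL.

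**Step 2. Size of the discrepancy.** 100 / 10 = 10, and 100 / 9.09 = 11. The printed value is 10 to 11 times the true concentration of the bag.

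**Step 3. What the rest of item 2 implies.**

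- Volume in 10 minutes: 600 mL/hr × 10/60 hr = 100 mL.
- Concentration needed for 1 g in that volume: 1000 / 100 = 10 mg/mL.
- If the bag really were 100 mg/mL, 100 mL would carry 100 × 100 = 10,000 mg, ten times the ordered dose.

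The dose, time and rate therefore agree with the nominal mixture and not with the printed label.

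**Step 4. If staff follow the printed steps.** In 10 minutes at 600 mL/hr they give 100 mL × 10 mg/mL = 1000 mg, or 100 mL × 9.09 mg/mL = 909 mg. The shortfall in the second case comes from the added vial volume, not from the wrong label. Running the whole 110 mL takes 110 / 600 × 60 = 11 minutes and gives the full gram.

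**Step 5. If someone works from the printed concentration (hypothetical).**

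- Volume taken as 1 g: 1000 / 100 = 10 mL.
- Rate to give it in 10 minutes: 10 mL × 6 per hour = 60 mL/hr.
- Drug actually given: 10 × 9.09 = 91 mg, or 10 × 10 = 100 mg, which is 9.1% to 10% of the ordered dose.
- If only the rate is set this way and the bag runs to the end: 100 / 60 hr = 100 minutes, or 110 / 60 hr = 110 minutes, instead of 10.

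**Step 6. Upper limit.** The bag contains one vial, so it cannot deliver more than 1 g.

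**The case against.** The strongest defence is that the parenthesis merely repeats the vial strength. On that reading the number is true and only its position is wrong, and the conflict with the pump rate disappears. The reading is possible. It is not the natural one, because the figure follows the diluent and the vial strength is already given earlier in the line. Even if it is what the authors meant, the line misleads and needs correcting.

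A second objection is that no printed step uses the concentration. Vial, diluent, dose, time and rate are all stated, so the infusion can be prepared and given without it. To under-dose, someone would have to set aside the explicit 600 mL/hr, recalculate a rate, pass the two-person check and stop after about a tenth of a bag known to hold the whole dose. The document does not say that pumps are programmed by concentration. This objection stands: the under-dosing and slow-infusion figures are what-if values, and the check in item 5 may well catch such a mistake, since 60 mL/hr conflicts with the printed rate.

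Third, the institutional policy may state the right concentration. That cannot be determined from the document, and it would not correct what Supplement A prints.

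These points limit the consequence. None of them makes 100 mg/mL the concentration of the prepared bag.

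**Conclusion.** The concern holds as a minor error, with high confidence. The concentration printed after the dilution step matches the undiluted vial and overstates the prepared bag by a factor of 10 (final volume 100 mL) to 11 (final volume 110 mL). Which end applies depends on whether saline is withdrawn before mixing, which the plan does not say.

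The firm finding is a wrong or misplaced number in an operative drug-preparation instruction, in conflict with the dose, time and rate beside it. Any dosing consequence rests on the assumption that someone uses the printed concentration. An overdose from a single bag is ruled out. The sample size, the definition of the endpoint and the analysis do not depend on this figure.

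**What to change.** In Supplement A, item 2, replace the parenthesis with a final concentration of about 10 mg/mL, or with about 9.1 mg/mL in 110 mL if no saline is withdrawn. State the final volume so that the figure can be checked.

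Separately, and optionally, say that the whole bag is to be infused, noting that 110 mL at 600 mL/hr takes about 11 minutes.

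The cost is a one-line text correction. The ordered dose, pump rate, sample size and analysis stay as they are.

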 2. INTRAOP REPORT-OB
 3. SURGICAL/PROCEDURAL CHECKLIST
 4. Pre-Op Checklist (unless emergent C/S)

- G. OB Nurse Teach and Discharge Plan
- H. OB Nurse Transfer report*
- I. 24 Hour Nursing Narrative
- J. Postpartum Progress Note
- K. OB MultiD Discharge Summary
